#### 1.2.1 *Overview of Systemic Lupus Erythematosus*

Systemic Lupus Erythematosus (SLE) is an autoimmune disease with unknown etiology. It is of great clinical variation as it can affect virtually all body systems including musculoskeletal, mucocutaneous, cardiovascular, neurological, respiratory, renal, ophthalmic, hematological and gastrointestinal systems.

#### 1.2.2 *Polyarthritis in Lupus Patients*

Inflammatory polyarthritis is common in systemic lupus patients, with swollen, tender joints occurring in up to 88% . Although SLE arthritis is generally less destructive than rheumatoid

arthritis, joint deformities similar to rheumatoid arthritis can occur in 25-35% of SLE patients. Erosions detectable on standard x-rays occur in approximately 4%. However, in multiple studies, high-resolution ultrasound and/or power Doppler of the wrists, MCPs and PIPs in SLE patients with hand arthritis showed synovitis in 70-95% depending on joint studied (synovitis was most abundant in wrists), erosions in approximately 50% (particularly in MCPs) and tenosynovitis in 65%.

Lupus arthritis can cause pain, stiffness, swelling, tenderness, and warmth of joints in a waxing and waning pattern. Several joints may be involved at the same time and all major and minor joints may be affected.

There is no definitive treatment or cure for lupus polyarthritis. Standard of care for patients with lupus such as corticosteroids, NSAIDs, anti-malarials, and immunosuppressive drugs and biologics treat lupus polyarthritis as well as other SLE symptoms. These treatments, however, especially immunosuppressive medications, have many side effects, including infectious complications.

The PI recently reviewed 10 patients with lupus arthritis she examined serially. On a 66-joint tender/swollen joint count, the average score was 21. In two patients who had just completed 12-week-long open clinical trials and who reported improvement, counts dropped from 22-31 to zero-4. Thus, arthritis is an important component of SLE and can easily be quantitated by experienced investigators to assess benefits of interventions. We are proposing here to use a standard 28 joint count, which includes the joints most frequently involved in SLE (hand 1-5 PIPs, 1-5 MCPs, wrists, elbows, knees). Reliability of these joint counts (28 joints) has been well documented in patients with rheumatoid arthritis, the 28 joint count is standard in clinical investigations in RA, and the ultrasound examination for synovitis proposed here will examine the hand (PIP2-5, MCP 2-5) and wrist joints. Change in joint counts can be evaluated as a dichotomous variable (as we are proposing for the primary outcome measure), or as a continuous measure to increase sensitivity. In addition, as a secondary outcome we are proposing use of the Clinical Disease Activity Measure (CDAI) which is also a continuous variable. We have not used CDAI in studies of lupus arthritis, but a recent publication reports that the CDAI responded favorably to abatacept therapy in 6 of 6 patients with rhupus – an overlap syndrome between rheumatoid arthritis and systemic lupus. In RA, CDAI (a sum of swollen joints, tender joints, physician global assessment and patient global assessment) correlates well with DAS28, ACR response rates 20/50/70, HAQ scores and radiographic changes over time. It has the advantage of not requiring laboratory assessments and thus can be done at the patient visit.

### **1.2.3        *Role of T cells in Systemic Lupus Erythematosus***

The arthritis of SLE, like RA, is an inflammatory synovitis. Histology, cell infiltrates and gene expression in synovial specimens from patients with SLE, RA and osteoarthritis were compared in a recent study. SLE arthritis was characterized by proliferation of synovial lining cells (less than in RA), diffuse mononuclear cells infiltrating into the synovium, and perivascular mononuclear cell infiltrates. Infiltrating cells include CD3+ T cells, CD8+ T cells, CD20+ B cells, CD68+ macrophages and CD138+ plasma cells. Nearly half of the genes dysregulated in RA synovial tissue related to T and B cell functions; nearly half in SLE were interferon-regulated genes and STAT1 (in the IFN pathway). Since clinical disease in SLE is initiated by autoantibodies and immune complexes which deposit in target tissues, activate complement, and initiate inflammation, the role of B cells is central in the disease. Increases in circulating mature B cell subsets, such as

memory B cells, activated B, plasmablasts and short-lived plasma cells are characteristic. Since most pathogenic autoantibodies and immune complexes contain IgG, and T cell help is required for Ig switch from IgM to IgG, T cell help is critical for sustaining many autoreactive B cells and promoting their differentiation to autoantibody-secreting plasma cells. Helper CD4+ T cells can secrete IFNgamma or IL-17. Therefore, interfering with T cell activation and thus T cell help by administering abatacept should reduce B cell stimulation and therefore reduce quantities of autoantibodies and possibly of total IgG. In this study, we propose to determine biological consequences of treatment with abatacept, which might include 1) decrease in numbers of activated CD4+CD25- T cells and in those cells that stain for IFNgamma or IL-17; 2) increased numbers (measured as CD4+CD25+Foxp3+ and CD8+Foxp3+ peripheral blood cells) and/or function of Tregs (measured as ability of CD4+CD25hi T cells to suppress proliferation of autologous CD4+CD25- T cells); 3 ) decreased plasma levels of IFNgamma, IL17 and IL23, with increased levels of IL10 and TFGbeta. 4) decreased numbers of activated B cells and plasmablasts; 5) decreased quantities of total IgG, and IgG anti-DNA; 6) increased plasma levels of BLyS in response to lower numbers of activated/mature B cells and plasmablasts. Any of these features would indicate a biologic effect of abatacept, whether or not those effects correlate with clinical outcomes.

Recent data, published in abstract form, from other institutions performing clinical trials of abatacept in SLE suggest that responders can be differentiated from non-responders by 1) transcriptome differences in mononuclear cells at baseline, and 2) interferon signatures at baseline, based on changes in expression of genes induced by interferons (Bandyopadhyay S et al, De-convolution of whole blood transcriptomic data from a phase IIb, randomized, double-blind, placebo-controlled trial of abatacept in systemic lupus erythematosus. 2015 ACR/ARHP Annual Meeting, abstract number 2067.)

Most importantly, the treatment should suppress disease activity. In the published phase III trial of abatacept in SLE (without active nephritis), overall disease activity suppression occurred in both placebo and abatacept groups, but the group with polyarthritis had a significantly fewer flares with abatacept than with placebo.

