#### **Secondary Objectives:**

1. Mean and median joint scores in treated vs placebo patients at 16 weeks, compared to baseline scores.
2. Proportion of patients who achieve improvement in SLEDAI 2K at 16 weeks of >3 points, comparing abatacept to placebo.
3. Proportions of patient who do not worsen by PGA score ( $\leq 0.8$  change from initial PGA score on 3 point line).
4. Mean and median changes in CDAI comparing abatacept to controls at 8, 12 and 16 weeks.

5. Changes in a) synovitis, b) tenosynovitis and c) erosions measured by high-energy ultrasound with Doppler flow at zero, and 16 weeks, compared to placebo.
6. Steroid sparing effect of abatacept, measured as ability to taper prednisone to <10mg/day by week 16 comparing abatacept-treated subjects to placebo-treated subjects.
7. Change in fatigue from baseline to 16 weeks as measured by the FACIT fatigue score instrument
8. Change in quality of life comparing baseline to 16 weeks as measured by the SF 36.
9. Safety, measured in standard methods as AE and SAE, including likelihood that the AE/SAE was related to the study biologic.
10. Time to response, measured as joint counts (sum of tender and swollen joints) at zero, 4, 8, 12, and 16 weeks.
11. Change in peripheral blood T cell compartments indicating decline in pro-inflammatory profiles, i.e., we expect decrease in CD4+ effector T cells that make IFNgamma (TH1) and IL-17 (TH17) and increase in ratio of Treg to Teff, as well as decreased function of Thelper and increased functions of Tregs. CD4+CD25+ Foxp3+ and CD8+Foxp3+ will be the definition of regulatory T cells. These will be measured at baseline and 16 weeks
12. Change in anti-DNA and total IgG levels, as well as rise in serum complement levels as disease improves and fewer B cells are activated: measure these at zero, 8 and 16 weeks.
13. Effects of abatacept on serum levels of BLyS (BAFF). As numbers of activated B cells and plasmablasts fall, we expect an increase in BLyS levels. Measure at baseline and 16 weeks.
14. Changes in transcriptome in whole blood and/or purified mononuclear cells in peripheral blood, and changes in interferon-induced gene expressions at baseline that may predict response or non-response at 16 weeks. Measure at baseline and last study visit.

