### ***8.4.3 Efficacy Analyses***

The Fisher's exact test will be used to compare the percent of subjects achieving primary and secondary outcomes between two groups. Wilcoxon rank sum tests will be used to compare ordinal and quantitative outcomes between groups. Logistic regression will also be used to adjust for baseline clinical presentation and demographic factors. A site by treatment interaction effects will be included in the model to account for possible differences in treatment efficacy between our two sites. Bivariate analysis and nonparametric analysis (for example local polynomial regression or generalized additive model analysis) will be carried out to inspect the relationship between outcome and covariates. The goodness-of-fit of logistic models will be evaluated using the Hosmer-Lemeshow test. With the quantitative outcomes such as joint counts, ultrasound measurements, etc we will use Poisson regression to assess the treatment effect or linear regression for continuous outcomes. Poisson regression is a special case of generalized linear model and robust pseudo likelihood inference will be used in the analysis. We also will use multiple imputation technique to accommodate possible missing data at 12 and 24 weeks due to patients lost to follow up. The imputation model will include all baseline 12 week and 24 week outcomes and covariates to impute the missing outcomes . Analyses will be done with and without imputation.

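### Section 1.2.3 lets any one of 16 directional immune markers indicate a biologic effect, with no threshold or multiplicity control; with no true effect, 5% tests would still support it in up to about a third of trials.

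*Combined protocol and SAP*

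**What the plan says.** Section 1.2.3 sets out what the sponsor expects abatacept to do to the immune system, in six numbered groups:

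1. Effector T cells, three markers: "decrease in numbers of activated CD4+CD25- T cells and in those cells that stain for IFNgamma or IL-17" is the predicted change.
2. Regulatory T cells, three markers: higher CD4 and CD8 Foxp3-positive counts, or stronger suppressive function.
3. Cytokines, five markers: "decreased plasma levels of IFNgamma, IL17 and IL23, with increased levels of IL10 and TFGbeta" is the prediction here.
4. B-lineage cells, two markers: lower counts of the activated cells and of the plasmablasts.
5. Antibodies, two markers: "decreased quantities of total IgG, and IgG anti-DNA" is what the sponsor expects.
6. BLyS, one marker: a rise in its plasma level.

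The section then states how such results are to be read: "Any of these features would indicate a biologic effect of abatacept, whether or not those effects correlate with clinical outcomes".

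Most of these markers return as secondary objectives in Section 2, for example "Change in peripheral blood T cell compartments indicating decline in pro-inflammatory profiles", and as secondary assessments in Section 6.4.2. Neither section gives a criterion for calling a change real. Section 8.4.3 supplies the test: "Wilcoxon rank sum tests will be used to compare ordinal and quantitative outcomes between groups". It states no adjustment across outcomes and no hierarchy. Section 8.4.4 (Other Analyses) is marked not applicable. The only significance level in the plan is the 0.05 used in Section 8.1 for the primary endpoint.

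**The concern.** An inference drawn from any one of many results is only as reliable as the whole set. With 16 chances and no adjustment, an isolated positive marker is a common outcome for an inert drug. The sentence also says that agreement with clinical outcome is not required, which removes the one outside check on a chance finding. It does not say whether a change is judged against placebo or only against the patient's own baseline.

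What is at stake is the mechanistic conclusion. A report that follows the text could state that abatacept was biologically active on evidence that cannot separate an active drug from an inactive one.

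**Working it through.** **Inputs from the documents**
- Marker count from the six groups in Section 1.2.3: 3 + 3 + 5 + 2 + 2 + 1 = 16. Ten are predicted to fall (3 + 0 + 3 + 2 + 2 + 0) and six to rise (0 + 3 + 2 + 0 + 0 + 1).
- Test: between-group Wilcoxon rank sum (Section 8.4.3).
- Sample: 64 patients, 32 per arm. The synopsis places the correlative studies at UCLA only, which is 32 patients, or about 16 per arm if the arms are balanced within site (assumption). Section 6.4 says samples come from all subjects.

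**Assumptions**
- A two-sided 5% level per marker, because the plan gives none for markers.
- Correlation between markers of 0 to 0.7, because the plan gives no figure.

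**The plan's own figure.** The plan states no error rate for this inference. Its one related calculation is the primary sample size. With 67% v 30%, mean 0.485, 5% two-sided and 80% power:

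n = [1.960 × √(2 × 0.485 × 0.515) + 0.842 × √(0.67 × 0.33 + 0.30 × 0.70)]² / 0.37² = (1.385 + 0.553)² / 0.1369 = 27.4, so 28 per group, as stated.

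A one-sided test would give 22. The plan's 0.05 is therefore two-sided, which supports the same convention for the markers.

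**Independent markers, no true effect**
- Predicted direction only (0.025 per marker): 1 − 0.975^16 = 33.3%.
- Either direction (0.05 per marker): 1 − 0.95^16 = 56.0%.
- Any numerical shift in the predicted direction, no test: 1 − 0.5^16, above 99.9%.

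**Correlated markers.** Simulated as Z_j = √ρ·F + √(1 − ρ)·e_j for 16 markers (200,000 draws), with ρ aligned to the predicted directions:

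| Assumed ρ | 5% test, predicted direction | 5% test, either direction | No test, predicted direction |
|---|---|---|---|
| 0 | 33% | 56% | >99.9% |
| 0.3 | 24.5% | 47.5% | 98% |
| 0.5 | 19% | 37% | 94% |
| 0.7 | 13% | 26% | 86% |

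If the raw markers are positively correlated whatever their predicted direction, the predicted-direction rate at ρ = 0.5 is about 25% instead of 19%. This gives the range of 13-25% for ρ of 0.5-0.7.

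**Sensitivity**
- With 16 per arm the Wilcoxon test runs slightly below nominal (actual size about 0.044). The independent figures become about 30% (predicted direction) and 52% (either). Whether samples come from one site or two therefore hardly matters for the false-signal rate.
- If each of the six groups were reduced to a single test: 1 − 0.975^6 = 14.1%, or 1 − 0.95^6 = 26.5%.

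**With adjustment.** At 0.05/16 = 0.003125 per marker, the chance of any false signal is 1 − (1 − 0.003125)^16 = 4.9% under independence, and lower with positive correlation.

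**The case against.** The sentence is in the Introduction, not the analysis plan. It follows a list of consequences that are only said to be possible, and no objective, assessment or analysis section repeats an any-of-16 rule. Section 6.4.2 interprets BLyS on its own, which suggests reading marker by marker. The synopsis calls these correlative studies, and Section 1.2.3 goes on to say that suppressing disease activity matters most. In a 64-patient trial, strict error control on correlative markers costs a good deal of power.

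Much of this stands, and it limits the point. Four stronger readings are tempting but not supported:
- *The plan treats one marker as proof.* The wording is that a change would indicate an effect, which is weaker.
- *The inference fails about half the time or more.* All 16 markers have a predicted direction, so a two-sided 5% test gives at most about a third. Half or more needs either-direction counting with weakly correlated markers, or no test at all. The text sets no threshold, so the no-test reading cannot be excluded, but it is not the only one.
- *The rate is always at least four times nominal.* At an aligned correlation of 0.7 it is about 13%, or 2.6 times 5%.
- *This would be the trial's main positive claim if the primary endpoint failed.* The documents do not say so, and several clinical secondary objectives are listed ahead of the markers.

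The objection does not remove the problem. The sentence is the only place that says what a positive marker result as a whole would mean, and no later section supplies a threshold, hierarchy or adjustment.

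**Conclusion.** The concern holds in limited form. The plan states an any-one-of-16 inference and gives it no error control. With no true effect and two-sided 5% tests counted in the predicted direction, it is false in about 33% of trials under independence and about 13-25% at correlations of 0.5-0.7. Counting either direction gives about 56% and 26-37%. Counting bare numerical shifts gives about 86% to nearly 100% over correlations of 0 to 0.7. These figures rest on the count of 16, an assumed 5% level per marker and assumed correlations. Within those ranges, no reading brings the rate near 5%.

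The primary endpoint and its conclusion are untouched. The defect concerns one interpretive claim about secondary and correlative measures. It deserves correction because it is cheap to correct and because, as written, it approves a claim that chance alone would often support.

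**What to change.** Replace the sentence in Section 1.2.3, and repeat the rule in Section 8.4.3, with:

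> An overall biologic effect will be concluded only if at least one prespecified marker differs between abatacept and placebo in change from baseline to week 16, in its predicted direction, after permutation max-T (or Holm) adjustment across the markers actually measured, at an overall 5%. Individual unadjusted marker results are exploratory and descriptive.

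State the sidedness of the overall 5% with it.

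Fix the family of markers before unblinding. The lists now differ: the synopsis adds serum IL-6 and cytoplasmic IL2 and IL21 and omits TGFbeta, whereas Section 1.2.3 and the baseline visit in Section 6.1 include TGFbeta. Section 6.4 also lets the marker set change as the literature develops.

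**Cost.** No new data or visits are needed. The overall claim loses power when only one marker moves. For a 1-SD effect on a single marker, going from an unadjusted two-sided 5% test to Holm's first step lowers power from about 75% to 30% at 16 per arm, and from about 97% to 78% at 32 per arm. A directional max-T procedure loses less.

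If the sponsor does not want that cost, delete the any-of-these inference and label all marker results exploratory. That also removes the defect.

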### **1.3 Summary of Results of Investigational Program in Rheumatoid Arthritis**

The initial efficacy and safety of abatacept (previously known as CTLA4-Ig and BMS-188667) was established in clinical studies of RA, psoriasis, and multiple sclerosis. The subsequent registrational program was in juvenile idiopathic arthritis (JIA), with data being collected from the ongoing long-term extension portion. Current active registrational programs for abatacept include studies in systemic lupus erythematosus (SLE) including lupus nephritis, and psoriatic arthritis.

A full development program conducted in adult RA led to regulatory approval in the United States for this indication in December 2005, in Canada in June 2006, and in Europe in May 2007. In the US, abatacept now has two indications: (1) treatment of moderate to severe active RA in adults, and (2) treatment of moderate to severe juvenile idiopathic arthritis (JIA) in patients who have failed prior therapy with disease-modifying anti-rheumatic drugs (DMARDs).

### **1.3.1        *Core Efficacy Studies of Abatacept in Rheumatoid Arthritis***

The RA clinical program consisted of five core studies: IM101-100, IM101-101, IM101-102, IM101-029, and IM101-031 (N=2944) . Each study had a double-blind placebo-controlled period of 6 months or 1 year. In Study IM101-100, subjects received abatacept 2 mg/kg, 10 mg/kg, or placebo. In the other studies, subjects received abatacept 10 mg/kg or a fixed dose that approximated 10 mg/kg or placebo.

Subjects who completed the double-blind period were offered entry into an uncontrolled, open-label period, in which all subjects received abatacept (in a fixed dose that approximated 10 mg/kg). A total of 2624 subjects in the core RA studies received the approved abatacept dose (10 mg/kg or a fixed dose that approximated 10 mg/kg) in the combined double-blind and open-label periods, representing 4603 person-years of exposure.

The efficacy of abatacept at a weight-tiered dose approximating 10 mg/kg was demonstrated in placebo-controlled studies in adult subjects with active RA and an inadequate response to methotrexate (IM101-100, IM101-102, and IM101-043), and in one study in adult subjects with active RA and an inadequate response to at least one TNF-blocking agent (etanercept and/or infliximab; IM101-029) . Other studies have provided additional supportive evidence of efficacy. Abatacept (10 mg/kg or a fixed dose approximating 10 mg/kg) was significantly more effective than placebo in reducing the signs and symptoms of RA, including induction of major clinical response, improving physical function, slowing the progression of structural damage, and improving the quality of life in subjects with moderately to severely active RA.

In Studies IM101-102 and IM101-029, improvement in signs and symptoms assessed by the American College of Rheumatology (ACR) 20 response rate versus placebo was observed after administration of the first dose, as measured at Day 15, and it was maintained through the double-blind study phase and for up to 3 years (in IM101-029 and IM101-102) and up to 5 years (in IM101-100). In the open-label extensions of IM101-100, IM101-102, and IM101-029, durable and sustained ACR20, ACR50, and ACR70 responses have been observed through 48, 24, and 18 months, respectively, of abatacept treatment .

### **1.3.2        *Pharmacokinetics of Subcutaneous Formulation***

#### **Subcutaneous (SC) formulation in adult population**

Single SC doses of abatacept (50 to 150 mg) demonstrated approximately dose proportional PK in healthy adult subjects. Following administration of single doses of 50 to 150 mg of abatacept, the mean Cmax increased from 3.5 to 10.7 µg/mL and the geometric mean AUC(INF) increased from 1490 to 4270 µg·hour/mL. The median time to occurrence of Cmax (Tmax) following SC administration ranged between 48 and 168 hours. Mean T1/2 values in healthy subjects ranged from 11.2 to 14.7 days. T1/2 values from this study were comparable with the T1/2 values obtained with abatacept administered IV to subjects with RA (13 to 14 days) 30. The fact that T1/2 values following SC dosing were comparable to T1/2 values obtained after IV dosing suggests that the elimination characteristics of abatacept were not altered following SC administration.

A double-blind, randomized, placebo-controlled, parallel-group, multiple-dose study (IM101063) assessed the steady-state trough serum concentrations of abatacept following SC administration in

subjects with RA. Subjects were randomized to receive either abatacept or placebo in 1 of 5 parallel groups based on body weight obtained at the screening visit (Table 1.3.2). The SC dose regimens were selected to target trough levels between 10-30 ug/ml, which was associated with efficacy with the IV formulation.

